7.1. Study Subjects

7.1.1. Disposition of Subjects

Subject disposition will be presented in a listing, and will include age, gender, date of consent, date and dose of first infusion of study drug, date and dose of last infusion of study drug, date of completion or premature discontinuation from the study, and reason for discontinuation if the subject discontinues prematurely. Data from all screened subjects will be included in the summary of subject disposition. The frequency and percentage of subjects who are treated and not-treated in the study, continuing treatment at the time of the analysis (for Week 96 analysis only), completed the study, and discontinued from the study, along with reasons for discontinuation, will be summarized. In addition, the number of subjects with at least one infusion during the treatment period (Week 0 to Week 96), and the number of subjects with at least one infusion in the extended treatment period (Week 97 to Week 144) will be presented.

7.1.2. Protocol Deviations

Protocol deviations will be listed by subject, as applicable.

7.1.3. Demographics and Medical History

All demographic and medical history information will be summarized using the FAS set.

7.1.3.1. Demographics

The following demographic variables will be summarized:

- Age (Years) reported to 1 decimal place (i.e. xx.x years), <12, ≥12 years, and 2-4 years
- Sex
- Race
- Ethnicity
- If Asian, Japanese (yes/no), and generation (first, second, third)
- Birth weight (kg), for subjects <4 years old at enrollment

By-subject listings of demographic information will be produced.

7.1.3.2. Baseline Characteristics

Summaries of baseline height (cm), weight (kg), and BMI (kg/m²) will be presented, as well as disease history. Disease history will include time since diagnosis (years), method of diagnosis, and whether any family members have been diagnosed with LAL-D.

7.1.3.3. Medical History

Baseline medical history information, i.e., number (%) of subjects who have a medical history will be summarized for the FAS. Summaries will be presented as prior disease and concomitant disease, with the prior and concomitant status determined by whether the condition was active (yes/no) at the time of screening. By subject listings will be created for medical history which will include medical history condition, start and end date, and if ongoing.

7.1.3.4. Baseline LAL Enzyme Activity and DNA Results

The number and percentage of subjects with LIPA gene sequencing results consistent with LAL-D and with fibroblast results consistent with LAL-D will be presented. In addition, the number and percentage of subjects homozygous for common mutation, heterozygous for common mutation, with another mutation, or no variants found will be presented. LAL Enzyme Activity at baseline will be categorized as affected (<=0.016 nmol/punch/hr), carrier (0.017 to 0.026 nmol/punch/hr); and unaffected (0.027 to 0.0152 nmol/punch/hr) are summarized.

7.1.4. Prior and Concomitant Medications/Treatments

Medications will be coded using the World Health Organization Drug Dictionary version in use by Alexion at the time of analysis. Summaries will be performed on the FAS.

The number (%) of subjects using prior and concomitant medications will be summarized for the World Health Organization Anatomical Therapeutic Chemical (WHO ATC) Class code and generic name. Subjects with multiple medications in the same class code will only contribute once to the number and percentage of subjects with a medication in that class; likewise, subjects with multiple entries for the same medication will only contribute once to the summary of the generic name.

Similar tables will be provided for lipid-lowering medications. However, in this case, prior lipid-lowering medications will be limited to medications administered in the period 6 weeks prior to the first study drug infusion.

In addition, the number of subjects using any lipid-lowering medication at baseline and post-baseline will be summarized along with a summary of whether post-baseline use of LLM was accompanied with a change in dosing (yes/no).

All prior and concomitant medications and treatments (pharmacological and non-pharmacological) will be provided in a data listing. The data listing will include start and end dates (or indication of ongoing), dose, unit, frequency, route, and an indication of whether the medication usage is prior, concomitant or both.

7.1.5. Modified Diet

The number and percentage of subjects on any low cholesterol or low saturated fat diet at baseline will be summarized along with the number and percentage of subjects on reduced consumption of fatty dairy products, non-dairy animal-derived fatty foods, and/or increased consumption of cholesterol lowering foods.

7.2. Safety Analyses

No formal hypothesis testing is planned. Baseline is defined as the last available assessment prior to the first infusion of SBC-102. In case of multiple pre-treatment measurements, Baseline is the average of the last (up to 3) measurements.

Listings of all safety data will be produced. Results from pregnancy tests will be presented in subject listings.

The analysis of safety and tolerability will include the following data:

- SBC-102 exposure.
- Adverse events.
- Clinical laboratory investigations.
- Vital signs (body temperature, pulse rate, respiratory rate, blood pressure).
- Physical exam.
- 12-Lead ECG.
- Concomitant medications and therapies.
- Antidrug antibody formation.

As sample size permits, safety analyses stratified by ADA status, and for other subgroups of interest might be explored.

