| | 
Changes and percentage changes from baseline, if applicable, will be summarized at each planned assessment time point using these general techniques.
 
The general techniques will be used to describe:
 
 • Demographics and baseline characteristics; • Subject accountability • Clinical laboratory tests (shift tables indicating changes relative to reference ranges may be constructed for some parameters; spaghetti plots of values over time may also be constructed) • Results of MRI assessments (spaghetti plots of values over time may also be constructed) • Physical exam and ECG data • Denver-II Assessment • Concomitant medication use • HRQOL 
Safety Analyses
 
Safety will be examined for the Full Analysis Set overall and, as subject numbers permit, stratified by dose, by ADA status, and for other subgroups of interest.
 
Adverse Events
 
AEs will be coded to system organ class and preferred term using the Medical Dictionary for Regulatory Activities. All AEs, SAEs, and IARs will be listed; separate listings will also be provided for subjects who die while on study and who discontinue sebelipase alfa due to an AE. The number and percentage of subjects experiencing any AE, any related AE, any SAE, any related SAE, and any IAR and deaths and any other discontinuations due to an AE will be tabulated.
 
Frequency of treatment-emergent AEs, SAEs, and IARs will be tabulated by preferred term within the system organ class. Frequencies will also be presented by the classifications of severity and causality within dose. In addition, frequency of AEs, SAEs, and IARs will be presented for time periods spanning the entire course of sebelipase alfa treatment: up to 24 weeks after the first dose, > 24 to 48 weeks, > 48 to 72 weeks, and > 72 to 96 weeks. As appropriate, additional listings, summary tables, and graphics will be generated to evaluate IAR frequency and severity over time. The incidence of AEs leading to study discontinuation will be summarized.
 
Anthropometric Parameters
 
Anthropometric indicators of growth status (WFA, plus additional parameters if sufficient data are available) will be evaluated for subjects < 18 years of age. Weight-for-length/weight-for-stature and body mass index, if computed, will be derived from data on weight and length/stature. Anthropometric parameters will be plotted on standard growth curves. Z-scores and percentiles based on the age-gender standardized norms will be calculated in accordance with the methodology described by the WHO (subjects ≤ 24 months) or CDC (subjects > 24 months to 18 years) and using the growth charts relevant to the respective methodology. The primary means for describing the impact of sebelipase alfa
 |

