8.7. Safety Analyses

Safety will be examined for the Full Analysis Set overall and, as subject numbers permit, stratified by dose, by ADA status, and for other subgroups of interest.

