8.7.1. Adverse Events

Adverse events will be coded to system organ class and preferred term using the Medical Dictionary for Regulatory Activities. All AEs, SAEs, and IARs will be listed; separate listings will also be provided for subjects who die while on study and who discontinue the study due to an AE. The number and percentage of subjects experiencing any AE, any related AE, any SAE, any related SAE, and any IAR and, deaths and any other discontinuations due to an AE will be tabulated.

Frequency of treatment-emergent AEs, SAEs, and IARs will be tabulated by preferred term within the system organ class. Frequencies will also be presented by the classifications of severity and causality. In addition, frequency of AEs, SAEs, and IARs will be presented for time periods spanning the entire course of treatment with sebelipase alfa: up to 24 weeks after the first dose, > 24 to 48 weeks, > 48 to 72 weeks, > 72 to 96 weeks. As appropriate, additional listings, summary tables, and graphics will be generated to evaluate IAR frequency and severity over time. The incidence of AEs leading to study discontinuation will be summarized.

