8.8. Efficacy Analyses

Efficacy will be examined for the Full Analysis Set and, as subject numbers permit, stratified by dose, by ADA status, and for other subgroups of interest.

Efficacy of sebelipase alfa is expected to be reflected through changes in liver and spleen fat content and organ volume, clinical laboratory data and, where applicable, growth parameters. Evaluation of change in parameters will be made from key assessment time points to the pre-dosing baseline and, as appropriate, to dose-specific baseline assessments (i.e., the assessments taken just prior to escalation to a higher dose level). Additional comparisons of change between sequential assessment time points may also be made.

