7.2.2.1. Overall Summary of Adverse Events

All TEAEs will be presented using summary statistics (n and n, %), showing the number of events as well as the number and percentage of subjects with the event.

Table 4: Subcategories For Treatment-Emergent Adverse Events (TEAEs)

Relationship
Related AEs
Not Related AEs
Severity
Mild
Moderate
Severe

The relationship between an AE and the study drug will be assessed as: not related; unlikely related; possibly related; or related. Subjects with at least one related AE and subjects with at least one not related AE will be summarized. Related AEs will include those AEs considered 'possibly related' or 'related' by the investigator; and not related AEs will include those AEs considered 'not related' or 'unlikely related'. The severity or intensity of the severity will be assessed and summarized as mild, moderate, or severe.

The number and percentage of subjects with an event meeting these criteria will be summarized according to the most severe occurrence of an AE for summaries of severity or intensity, and the most extreme relationship of the AE for summaries of relationship to study drug. The number of events will be summarized as reported, with no accounting for the most extreme severity or relationship. Additionally, the number and percentage of subjects who withdrew from the study due to an AE or who died on study will be presented along with the number of events meeting each of these criteria. These statistics will be prepared for all TEAEs and, separately, for SAEs and IARs.

7.2.2.2. AEs, SAEs and IARs by System Organ Class (SOC) and Preferred Term (PT)

The frequencies of TEAEs, SAEs, IARs and percentage of subjects with events will be tabulated by PT within SOC. Subjects are counted once in each SOC and PT. Percentages will be based on the total number of subjects in the specific analysis population. SOCs will be listed in order of frequency of occurrence.

Frequencies will also be presented by the classifications of severity and causality (i.e., relationship to study drug). The incidence of AEs leading to study discontinuation and SAEs leading to discontinuation will also be summarized.

A listing of IARs will be presented for those subjects who had a change in dose. This listing will include the subject number, and the prior dose administered, in addition to the standard adverse event listing elements.

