7.3. Efficacy Analyses

Efficacy will be examined for the FAS and, as subject numbers permit, stratified by ADA status, and for other subgroups of interest. Summaries will be provided in the event that at least 5 subjects are included in each subgroup defined by a characteristic (eg. at least 5 subjects with ADA positive and ADA negative).

Efficacy of SBC-102 is expected to be reflected through changes in liver and spleen fat content and organ volume, clinical laboratory data and, where applicable, growth parameters. Evaluation of change in parameters will be made from key assessment time points to the pre-dosing baseline and, as appropriate, to dose-specific baseline assessments (i.e., the assessments taken just prior to escalation to a higher dose level). Additional comparisons of change between sequential assessment time points may also be made.

For continuous endpoints, the observed values, change from baseline and percent change from baseline at each time of assessment will be summarized, and will include 95% confidence intervals.

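### The SAP removes the protocol's conditional by-dose stratification without listing the change, so every planned adverse-event table pools events over doses that change within subject

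*SAP*

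**What the plan says.** **Safety.** Protocol 8.7 examines the Full Analysis Set overall and, "as subject numbers permit, stratified by dose, by ADA status, and for other subgroups of interest". The counterpart in SAP 7.2 is "As sample size permits, safety analyses stratified by ADA status, and for other subgroups of interest might be explored".

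**Efficacy.** Protocol 8.8: "Efficacy will be examined for the Full Analysis Set and, as subject numbers permit, stratified by dose, by ADA status". SAP 7.3: "Efficacy will be examined for the FAS and, as subject numbers permit, stratified by ADA status, and for other subgroups of interest".

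**Adverse-event tables.** The protocol synopsis says "Frequencies will also be presented by the classifications of severity and causality within dose". Protocol 8.7.1 stops earlier: "Frequencies will also be presented by the classifications of severity and causality". SAP 7.2.2.2 follows the shorter form.

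**Subgroups.** SAP 6 and SAP 7.12 name age, gender, lipid-lowering medication, mutation category, fibrosis or cirrhosis status and baseline ALT for efficacy. For adverse events they name age only. Neither names dose.

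**Declared changes.** Neither SAP 4.1 (changes from the protocol) nor SAP 4.2 (changes from the previous SAP) mentions removing dose.

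**The concern.** Safety is the primary objective, and dose is a within-subject variable. Everyone starts at 1 mg/kg every other week. Some move to 3 mg/kg every other week and then to 3 mg/kg weekly, and decreases are allowed (Protocol 6.1.1 to 6.1.3). A single incidence per preferred term, with all treated subjects as denominator, cannot show whether an event began on the starting dose or after escalation. Protocol 1.4.1 gives a reason to look: AUC and Cmax rose more than in proportion to dose between 1 and 3 mg/kg.

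SAP 4.1 also drops the table of adverse events by time interval. That removal is declared, but the table was the one remaining summary that could have shown indirectly whether events came later, when escalated dosing is found.

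**Working it through.** Neither document has a power or sample-size figure to reproduce, so the check is a comparison of texts plus simple arithmetic.

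**1. Is the removal declared?** SAP 4.1 has six items: urinalysis summaries, vital-sign changes around infusion, the threshold of 5 antibody-positive subjects, the growth population, the time-interval table and the percentage denominator. Dose is not among them. SAP 4.2 declares the restriction on antibody-stratified efficacy and two dose-related additions, but not the loss of dose strata.

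**2. What dose information remains?**

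| Output | SAP section | Gives an event summary by dose? |
|---|---|---|
| Concurrent dose on data listings | 7 | No; subject-level tracing only |
| Weeks on specific doses | 7.2.1 | No; a denominator that no event table uses |
| Exposure listing sorted within initial dose | 7.2.1 | No; all subjects share one initial dose |
| Reaction listing with prior dose | 7.2.2.2 | No; a listing, limited to subjects whose dose changed |
| Dose-specific baseline | 7.3 | Efficacy only, where judged appropriate; 9.4.5 derives only the pre-first-dose baseline |

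On the fourth row, the SAP wording is "A listing of IARs will be presented for those subjects who had a change in dose".

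**3. How far apart are the pooled doses?** Weekly amount = dose ÷ interval in weeks.
- 1 mg/kg every other week: 1 ÷ 2 = 0.5 mg/kg per week
- 3 mg/kg every other week: 3 ÷ 2 = 1.5, which is 3-fold
- 3 mg/kg weekly: 3 ÷ 1 = 3, which is 6-fold

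**4. How much time can fall above the starting dose?** With the first infusion at Week 0 and dosing every other week, the infusion after k infusions falls at Week 2k.
- Standard (k = 8, Protocol 6.1.1): Week 16; (96 − 16)/96 = 83%
- Accelerated (k = 4, Protocol 6.1.2): Week 8; (96 − 8)/96 = 92%

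These are the largest shares for a subject escalated at those times, not expected values.

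**5. What could pooling conceal?** The documents give neither the number escalated nor any event risk, so this is illustration only. Assume a 10% risk on the starting dose and a further 40% after escalation. The cumulative risk in an escalated subject is 1 − 0.90 × 0.60 = 46%. With e of N escalated, the pooled incidence is [(N − e) × 0.10 + e × 0.46]/N.
- N = 20 (the ceiling expected in SAP 9.3), e = 3 to 10: 15% to 28%
- N = 30 (Protocol 8.2), e = 3 to 10: 14% to 22%

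Neither assumed risk can be read from the pooled figure.

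**6. How precise would a by-dose row be?** SAP 7.3 and 7.12 require at least 5 subjects per subgroup, and SAP 7 uses exact binomial intervals. With 0 of 5 subjects affected, the upper 95% limit is 1 − 0.025^(1/5) = 52%.

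**The case against.** The strongest reply is that little firm was promised and little is lost. Several parts of it stand.

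- **The protocol's commitment was conditional.** Both body sentences depend on subject numbers. The unconditional wording is in the synopsis only and disagrees with Protocol 8.7.1. Protocol 8.11, the subgroup section, never named dose, so its absence from SAP 7.12 is not a deletion.
- **The SAP does not forbid by-dose work.** Other subgroups of interest remain open, SAP 7.13 allows post-hoc subgroups, and the listings let a reader trace each escalated subject. In a study of 20 to 30 subjects that is feasible.
- **A by-dose table would be sparse and confounded.** Step 6 shows the imprecision. Higher-dose time comes later, and escalated subjects are selected for inadequate response. Patient-time denominators remove neither problem.

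Small numbers alone do not explain the edit. Antibody status was kept as a stratifier although SAP 4.1 reports only 2 positive subjects, below the SAP's own minimum of 5.

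A reader might also infer that efficacy responses before and after escalation are simply pooled. The documents do not support that: SAP 7.3 keeps, as appropriate, comparison "to dose-specific baseline assessments (i.e., the assessments taken just prior to escalation to a higher dose level". What is missing is its derivation and a named output. Nor can a reader infer that reactions do cluster after escalation, because no document reports events by dose.

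**Conclusion.** The point holds for safety and, in a narrower form, for efficacy. The SAP removes dose from two sentences it otherwise carries over, does not declare this, and leaves all planned tables of adverse events, serious events and infusion-associated reactions pooled over regimens that differ up to 6-fold in weekly amount. For efficacy, the gap is the removed stratification and a dose-specific baseline with no derivation.

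The effect on reported results is unknown because it depends on the number escalated; if no one is escalated or reduced, nothing is pooled. The 83% and 92% shares assume infusions on schedule and escalation at the first standard or accelerated opportunity. The point does not rest on the illustrative risks in step 5. It should be corrected because it touches the primary objective and the data needed are already collected.

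**What to change.** 1. In SAP 7.2.2, assign each treatment-emergent event, serious event and infusion-associated reaction to the actual dose and regimen in use at onset. Protocol 7.3 records time as well as date for events within 24 hours of an infusion, which helps on the day of a change.
2. Tabulate subjects ever exposed, events, and events per patient-year (reactions per infusion) by that dose and regimen, using the weeks on dose from SAP 7.2.1. All subjects belong in the starting-dose denominator. Do not create a single reduced-dose stratum: under Protocol 6.1.3 a reduction can lead to 1 mg/kg weekly, 1 mg/kg every other week (the starting regimen) or 0.35 mg/kg every other week.
3. Where a stratum has fewer than 5 subjects, give a by-dose listing instead.
4. Derive the dose-specific baseline in SAP 9.4.5 and summarise change from it for escalated subjects.
5. Label all of this descriptive, naming the confounding with time on study and with selection for inadequate response.
6. If dose is still left out, say so in SAP 4.1 with the reason. Either way, note there how the synopsis and Protocol 8.7.1 were reconciled.

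The cost is SAP wording, one event-level derivation, one baseline derivation and a few tables, with no new data collection. The drawback is small cells with wide intervals. The disclosure alone costs a sentence.

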7.2.1. SBC-102 Exposure

Number of weeks in the study and number of study drug infusions received will be summarized overall and; any changes in dose will be described in listings, and may also be provided in tabular summaries.

Exposure to study drug (SBC-102) will be summarized overall doses for the following parameters: the total number of infusions attempted, the number of infusions completed both without and with a rate change or infusion interruption and the number of infusions where the entire infusion volume was not administered will be presented. In addition, a summary will be provided showing the number of weeks on specific doses.

A data listing will be presented, sorted by subject within initial dose of SBC-102, providing the dates, total planned and actual volumes of drug infused, infusion rate and duration of the each infusion along with any modification to the infusion.

7.2.2. Adverse Events and Infusion-Associated Reactions

Adverse Events (AE) will be coded by primary system organ class (SOC) and preferred term (PT) using the Medical Dictionary for Regulatory Activities (MedDRA) (version 15.1 or higher). AEs will be determined as occurring from the signing of informed consent and prior to the initiation of SBC-102 (pre-treatment AEs), or as on/after first dose of SBC-102 (treatment-emergent) as described in Section 9.4.7. Pre-Treatment Adverse Events (PTAEs) will be presented in listings only, and Treatment-Emergent Adverse Events (TEAEs) will be presented in summary tables and listings.

Study displays for TEAEs are described below.

